8.4.3 Management of Abnormal Mammograms

Annual mammograms are required in this patient group. If the mammogram is abnormal and further evaluation can be performed within 30 days, the subject can continue on study HRT. If evaluation takes longer, the study HRT will be discontinued and restarted when evaluation proves negative for carcinoma. If the mammogram is abnormal but not suggestive of cancer, the patient will be continued on study HRT and the appropriate follow up mammograms obtained.

8.4.4 Decision to Stop Study Medication

The site study gynecologist, in consultation with the patient's physician will make decisions on whether to stop study medication because of a gynecological adverse event or an increased risk of deep venous thrombosis (i.e., need for prolonged bed rest due to a fracture,

prolonged illness) . Unmasking the patient's treatment assignment is usually not necessary and should only be considered as a last resort.

9. QUALITY OF LIFE ASSESSMENT

9.1 Objective

The purpose of the quality of life assessment in the WAVE clinical trial is to monitor the qualitative consequences of hormone replacement therapy and/or antioxidant treatment in a group of postmenopausal women who have angiographically established coronary artery disease. The quality of life outcomes are not expected to be related to the primary outcome (change in MLD). They may, however, be related to mortality rate, and potential confounders such as treatment noncompliance, incidence of intercurrent catheterizations, and side effects of treatment.

9.2 Instruments

The following psychometrically established instruments will be administered to all patients at randomization and at the 18 and 30 month visits:

1. The Medical Outcome Study Short Form (MOS-36) (153)
2. The Center for Epidemiological Studies - Depression Scale (CES-D) (154)
3. The Seattle Angina Questionnaire (SAQ) (155)
4. The Duke Activity Status Index (DASI) (156)
5. The MOS - Sleep Questionnaire (157)

In addition, the SAQ and DASI, will also be administered at 3 months for those patients in the Effects of Hormone Replacement Therapy on Electrocardiographic and Scintigraphic Measures of Myocardial Ischemia Ancillary Study.

Comment [TBC3]:

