7.3 RANDOMIZATION

Women who have met all inclusion criteria and have none of the exclusion criteria, and who have signed the informed consent, will be scheduled for a randomization visit. Prior to the randomization visit all women who did not have a blood collection at the screening visit will be advised to fast for at least twelve hours prior to the visit. A blood sample will be collected for central analysis and a local sample for assessment of INR if needed. Data to be collected are indicated in Table 2.

Randomization to one of the four possible study groups (active HRT and placebo antioxidants, active HRT and active antioxidants, placebo HRT and active antioxidants, placebo HRT and placebo antioxidants) will be by a telephone call to the Study Coordinating Center. After confirmation of the patient's eligibility the SCC will issue a

unique patient identifier and medication codes that the clinical center coordinator will use to obtain the woman's study medications. The unique patient identifier will be used on all study forms, laboratory samples, angiograms and any other necessary study documents. Each woman will have a one in four chance of being assigned to each of the four study groups. Randomization will be stratified by clinical center (n=5) and by whether a hysterectomy has been performed. Each woman will be given a seven month supply of her study medications, a medication instruction sheet, a bleeding calendar for those women with a uterus, a bottle of Centrum Silver vitamins (if she requests it), and an appointment for the one month visit.

TABLE 2

WAVE Summary	Screening	Randomization	IM	3M	6M	12M	18M	24M	30M	36M	Exit
Consent	X										
Creat, trig, FSH (if needed)	X										
INR	Obtain at either visit		X								
Study Bloods	Obtain at either visit			X			X			X	
Ht/wt, BP, waist/hip	Obtain at either visit					X		X		X	
Randomization form		X									
Breast, pelvic, Pap, mamm, breast self-exam teaching	X					X		X		X	
Sign medical release	X					X		X		X	
Brachial reactivity	Obtain between consent and initiation of study medication			X							
Dipyridamole SPECT/ETT				X						X	
ECG		X				X				X	
Patient tracking form		X			Update as needed						
Bleeding calendar		X	X	X	X	prn	prn				
Dispense study meds		X			X	X	X	X	X		
Adherence assessment					X	X	X	X	X	X	X
Quality of Life		X		X			X		X		
Follow-up visit*					X	X	X	X	X	X	X
Angiogram	X										X
Physical exam		X				X		X		X	

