7.4.4 Annual Visits (at 12, 24, 36 months)

The participant will be asked to bring in all unused study medication and all other medications she has taken since the last study visit. At the 36 month visit, the participant will be asked to fast 12 hours before coming to the visit. During each annual visit, a designated individual will review and discuss any symptoms potentially attributable to either study medication. The coordinator or his/her designee will:

1. At the 36 month visit, draw fasting study bloods for processing and shipping to the central biochemistry laboratory. Feed participant if desired. At the 36 month visit (42 month for some women), obtain pre-angiogram bloods, if necessary;
2. Document any clinical outcomes that have occurred since the last visit and record current medications on a follow-up form;
3. Record study medication capsule/tablet count on follow-up form; dispense a new supply of study medication;

4. At the 12 and 36 month visits obtain an ECG;
5. Perform a breast examination, provide breast self-exam teaching, perform pelvic examination, obtain a Pap smear (if uterus present and none done within past 12 months) and complete the physical exam form;
6. Ask participant to sign a medical release. Make arrangements to obtain any mammogram report done within the past 12 months, or schedule a mammogram;
7. At the 36 month visit (42 month for some women), schedule the exit angiogram and the visit.
8. At the 36 month visit, perform appropriate assessments for patients in the Effects of Hormone Replacement Therapy on Electrocardiographic and Scintigraphic Measures of Myocardial Ischemia Study.

Comment [TBC2]:

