18.3 SECONDARY ENDPOINTS

- To examine the acute effect of study drug on coronary vasomotor tone. This will be done by comparing the degree of ischemic burden between the baseline study and three month nuclear stress test.
- To correlate baseline exercise perfusion study with initial patient symptoms and angiographic findings.
- To determine if initially positive perfusion scans predict subsequent patient symptoms, and clinically important outcomes. To determine the ability of the initial exercise perfusion study to select a subset of patients who receive greater benefits from study drugs in terms of angiographic progression, ischemic burden, symptoms, and cardiac event rates.
- To study the effects of hormone replacement therapy on the ECG changes during standard treadmill exercise testing.
- To examine the acute and chronic effects of study drug on exercise capacity, and to correlate this with patient reported functional status as measured by standardized questionnaires.

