18.4 SUBSTUDY PROTOCOL

- All women randomized to participation in the overall trial will be asked to participate in this substudy.
- Women will undergo exercise gated SPECT imaging within 7 days of randomization and prior to initiation of study drug. The exercise protocol will include use of a standard Bruce

protocol with gated SPECT myocardial perfusion imaging. Technetium 99 tomography will be performed at rest and following exercise with reinjection performed in patients with fixed defects.

- At three months, during one of their follow up visits, women will undergo repeat exercise treadmill test. For those women who had perfusion defects initially, a follow up gated SPECT perfusion image will also be obtained at this time point. Those women with negative perfusion scans at enrollment will undergo only exercise ECG testing at the three month time point.
- At completion of the protocol and prior to 3 year recatheterization, all women will undergo repeat Bruce treadmill testing and gated SPECT perfusion imaging. (see Figure 1)

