18.6 DATA ANALYSIS

The goal of this analysis is to examine the acute and chronic effects of hormone replacement therapy and antioxidants on direct vascular tone, ischemia, and treadmill variables using stress myocardial perfusion and function imaging. Each woman's perfusion defect size will be quantified as a percentage of the total area on a bulls eye plot on enrollment, three month, and three year gated SPECT perfusion studies. We can quantify the changes in magnitude of ischemic burden by treatment group using a simple linear regression model. We hypothesize that some will improve, some will worsen and some will show no change. If our evaluation of the data reveals a large group without change, we will consider a categorical analysis of the data. Additionally, we will control for interim non-protocol drug therapy. Comparing the enrollment study to the three year study will look at the ability of study drug to change ischemic burden by affecting atherosclerotic progression which is the primary endpoint of the substudy. Comparing the enrollment study to the three month study will look at direct effects of study drug on vascular tone and responsiveness.

New ECG changes in the absence of perfusion changes at the three month test will be analyzed by treatment group to examine the potential effects of drug therapy alone on ECG parameters. The initial stress perfusion image will also be compared with patient symptoms, and with angiographic findings at enrollment. The degree to which minor luminal narrowings can cause ischemic burden through functional or dynamic stenoses will be examined. Additionally, we will determine if abnormal perfusion scans at enrollment are predictive of future symptoms, angiographic findings, and outcomes. We will look at the ability of perfusion imaging to identify those women who benefit most from treatment in terms of ischemic burden, symptoms, and outcome.

Functional status and exercise duration may be affected by hormone replacement therapy. Enrollment treadmill tests will be compared to the those obtained at the three month and three year endpoint to look at the acute and chronic effects of drug therapy on exercise capacity. We will compare Bruce treadmill variables and estimated metabolic equivalents to responses on functional status questionnaires regarding activity levels in everyday life. Changes in functional status will be compared across treatment groups.

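### The substudy's three-year treadmill test has no concurrent functional-status questionnaire; the nearest is nominally six months earlier

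*Protocol*

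**What the plan says.** **Questionnaires.** Section 9.2 lists five instruments, among them the SAQ and DASI, which "will be administered to all patients at randomization and at the 18 and 30 month visits". For substudy women it adds one further time: "In addition, the SAQ and DASI, will also be administered at 3 months for those patients". In Table 2 (section 7.3) the "Quality of Life" row is marked at randomization, 3, 18 and 30 months. Its cells for 36 months and exit are empty.

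**Treadmill.** The "Dipyridamole SPECT/ETT" row of Table 2 is marked at 3 and 36 months, with a baseline test before study medication starts. Section 7.4.4, item 8, reads "At the 36 month visit, perform appropriate assessments for patients in the Effects of Hormone Replacement Therapy". Section 18.4 places the last test relative to the exit angiogram: "At completion of the protocol and prior to 3 year recatheterization, all women will undergo repeat Bruce treadmill testing and gated SPECT perfusion imaging".

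**Analyses.** Section 18.3 has as a secondary objective "To examine the acute and chronic effects of study drug on exercise capacity, and to correlate this with patient reported functional status". Section 18.6 compares the enrollment treadmill tests with those "obtained at the three month and three year endpoint to look at the acute and chronic effects of drug therapy on exercise capacity". It then plans to set Bruce treadmill variables and metabolic equivalents against the functional-status questionnaires.

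**The concern.** To correlate exercise capacity with reported function at a given time, both should be measured at about that time. The schedule does this for the acute question, because SAQ and DASI forms were added at 3 months for the women who have a treadmill test then. No such addition was made for the final test.

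A woman who has an infarction, a revascularization or a change of medication between her 30-month form and her final treadmill will have a treadmill result that reflects it and a questionnaire that does not. The chronic half of the objective in section 18.3 would then relate two measures of a possibly different clinical state. This has to be settled in the visit schedule, because an analysis plan cannot recover a form that was never given.

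**Working it through.** The protocol gives no sample size, power or precision figure for this correlation, so there is no figure to reproduce. The check sets the two schedules side by side for a substudy woman.

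| Time | Treadmill (Table 2, 7.4.4, 18.4) | SAQ and DASI (9.2, Table 2) | Concurrent pair? |
|---|---|---|---|
| Baseline | yes, within 7 days of randomization | yes, at randomization | yes |
| 3 months | yes | yes, substudy women only | yes |
| 18 months | no | yes | not needed |
| 30 months | no | yes | not needed |
| 36 months | yes | no | **no** |

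**Gap at the final test.** Taking the final treadmill at the 36-month visit, the gap is 36 - 30 = 6 months. Section 7.4.4 schedules the exit angiogram from the 42-month visit for some women, and section 18.4 ties the last treadmill to the time before recatheterization. If a woman's test were done at 42 months, the gap would be 42 - 30 = 12 months. Table 2 and item 8 of section 7.4.4 name 36 months, so six months is the nominal figure and twelve is a possibility for some women.

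**Does another passage supply the missing form?** The general reference to assessments in item 8 of section 7.4.4 might be read to include questionnaires. Section 7.4.2 uses the same kind of general reference for the 3-month visit, yet there section 9.2 and Table 2 still list the questionnaires explicitly. Where the forms are intended they are listed, and at 36 months they are not. Section 7.4 allows for 42- and 48-month visits, and no questionnaire is listed for those either.

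**Do the planned analyses need the form?** Section 18.3 refers to both acute and chronic effects on exercise capacity and to their correlation with reported function. Section 18.6 takes the chronic treadmill measure at three years. Together these imply a late pairing of treadmill with questionnaire, although no single sentence gives the questionnaire's time point. The comparison of changes in functional status between treatment groups, also in section 18.6, does not need a treadmill at the same visit and can use the 30-month form.

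**The case against.** The strongest reply is that no stated analysis becomes impossible. Neither 18.3 nor 18.6 says when the questionnaire for the chronic comparison is to be taken, and a form at 30 months is a usable late measure of function. The extra 3-month form also has a plain reason of its own: without it there would be no questionnaire between baseline and 18 months, and the acute question could not be addressed. Leaving out a 36-month form may have been a decision about burden. The substudy can be declined (section 7.2) and depends on outside funding (section 18.1).

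Most of this stands, and it limits the point to a weakened secondary analysis. It does not remove the gap, because the protocol states no rule pairing the 30-month form with the later treadmill.

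Two stronger readings are tempting, and the protocol supports neither.

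- A reader might infer that the acute and chronic correlations will be compared and that the schedule alone would produce a fall between them. No such comparison is planned in 18.3, 18.6 or 18.8.
- A reader might put a number on the loss. Assuming a six-month self-correlation of 0.7 to 0.9 for functional status, and multiplying the true correlation by it, gives a reduction of 1 - 0.9 = 10% to 1 - 0.7 = 30%. The approximate sample-size factor runs from 1/0.9² = 1.23 to 1/0.7² = 2.04. The self-correlation is wholly assumed. The formula supposes that the 30-month score relates to the final treadmill only through function at that later time. It also describes correlations of levels, while 18.3 concerns effects over time. With no target set for this correlation, the factor breaches nothing in the plan.

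**Conclusion.** The gap is real. For substudy women the final treadmill test has no concurrent SAQ or DASI. The nearest form is nominally six months earlier, and up to twelve for a woman tested at 42 months. The effect is to weaken the chronic half of one secondary objective in an optional substudy. How much it weakens it depends on how stable functional status is over the gap and how many women have an intervening event, and the protocol gives neither.

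The conclusion rests on reading 18.3 and 18.6 together as calling for a late treadmill-questionnaire pairing. The primary MLD analysis and the main quality-of-life analysis, which ends at 30 months by design, are not affected. Priority: minor.

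**What to change.** In section 9.2 and the quality-of-life row of Table 2, add the SAQ and DASI for substudy women at the visit of the final treadmill test: 36 months, or later if the test is later. Tying the forms to the test and not to month 36 avoids recreating the gap for women tested nearer a 42-month exit. State in 18.3 and 18.6 that these forms are used for the three-year comparison with treadmill variables. Keep the 30-month forms for the main quality-of-life analysis.

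The cost is two more short questionnaires for substudy women at a visit they already attend, plus the protocol wording.

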9.3 Response Shift Analysis

A potential difficulty in analyzing quality of life outcomes is that the basic metric a patient uses to make quality of life judgments may be affected by time, by the treatment or by adverse events: a patient's concept of what constitutes a "good" quality of life may evolve in the course of the trial. For example, a patient answering questions about how much her health limits

her activities may have very different expectations at baseline and at 30 months. She may describe her activities as very limited at baseline but, having adapted her daily routines and lowered her expectations over time, may report only minor limitations at 30 months even if, objectively, her status has changed little.

Because the patients' responses to the quality of life questions are subjective, it is important to determine whether the criteria they use to make quality of life judgments remain approximately constant over the course of the trial. If they do not, simple comparisons between the baseline and the follow-up responses will be misleading. The following procedure will be used to assess the extent of the change over time in the basic metrics used by the patients to make quality of life judgments:

- at the 30 month visit, after the patient completes the MOS-36 form, she will be asked to fill it out again from the point of view of how she felt at the time of the baseline visit. For patients whose criteria have remained fairly stable, this retrospective assessment should agree fairly well with the responses on the MOS-36 completed at baseline. If there have been significant changes in the criteria, however, the answers on the retrospective versions of the MOS-36 would be expected to differ significantly from those on the baseline versions.
- The difference between the baseline and the 30 month responses will be assessed using a separate statistical test for each question on the MOS-36. The test will be performed on the entire cohort and then in each of the following subgroups: the patients in each treatment group, the patients who had adverse events, and the patients who did not have adverse events. Adjustments will be made for multiple comparisons.

This approach, which is commonly used in educational research, is called a response-shift analysis (158). If significant differences between the baseline and retrospective answers are found within particular quality of life domains, all further analyses for those domains on the MOS-36 will compare the 30 month results to the baseline and to the retrospective analyses. Otherwise, only comparisons between the 30 month and baseline responses will be reported.

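### In protocol Section 9.3 the response-shift test is written for baseline versus 30 month answers, but the section's own procedure and decision rule need baseline versus retrospective answers

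*Protocol*

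**What the plan says.** All the relevant text is in protocol Section 9.3, Response Shift Analysis.

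- **Aim.** The section wants to know whether women's criteria for judging quality of life stay roughly constant. If they do not, it warns that "simple comparisons between the baseline and the follow-up responses will be misleading". Its example is a woman very limited at baseline who adapts and "may report only minor limitations at 30 months even if, objectively, her status has changed little".
- **First bullet (data and logic).** At 30 months, after the usual MOS-36, "she will be asked to fill it out again from the point of view of how she felt at the time of the baseline visit". If criteria have changed, "the answers on the retrospective versions of the MOS-36 would be expected to differ significantly from those on the baseline versions".
- **Second bullet (the test).** "The difference between the baseline and the 30 month responses will be assessed using a separate statistical test for each question on the MOS-36". It is to be run in the whole cohort, in each treatment group, and in women with and without adverse events. On multiplicity it says: "Adjustments will be made for multiple comparisons".
- **Closing paragraph (decision rule).** The rule is triggered as follows: "If significant differences between the baseline and retrospective answers are found within particular quality of life domains". In that case the 30 month results for those domains are compared with both the baseline and the retrospective answers. If not: "Otherwise, only comparisons between the 30 month and baseline responses will be reported".

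**The concern.** The first bullet and the decision rule both define response shift by the gap between the baseline form and the retrospective form. The second bullet, the only place where a test is specified, names a different pair. Taken at face value, the specified test feeds no rule, and the rule relies on a contrast for which no test sentence is written. The pair that is named is also the simple comparison that the section calls misleading when criteria have moved.

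An analyst who programs the second bullet as it stands and passes the result to the decision rule would be using the change score as the indicator of shift. A treatment that really altered quality of life could then be reported as having altered women's criteria. A shift running against a real change could go unnoticed, and the retrospective comparison would be left out for that domain.

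**Working it through.** **1. What '30 month responses' means in this section.** The retrospective form is also filled in at the 30 month visit, so the phrase could in principle refer to it. The closing paragraph decides against this. It lists the 30 month results, the baseline and the retrospective answers as three separate things, and its last sentence ("Otherwise, only comparisons between the 30 month and baseline responses will be reported") uses almost the same phrase for the current-state answers. The consistent reading of the second bullet is therefore current state at 30 months versus baseline.

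**2. What each contrast measures.** Let T0 be the baseline answer, *d* the real change and *s* the response shift. Ignoring recall error, which is an assumption of this model:

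- baseline = T0
- 30 month = T0 + d + s
- retrospective = T0 + s

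| Contrast | Measures | Role in Section 9.3 |
|---|---|---|
| 30 month − baseline | d + s | test in the second bullet |
| retrospective − baseline | s | first bullet and decision rule |
| 30 month − retrospective | d | extra comparison once a shift is found |

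Only the second row isolates the shift.

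**3. Illustration.** The protocol states no sample size, power or significance level for this test, so there is no figure of its own to reproduce. The inputs below are assumptions, except that 450 is the target sample size and 20% a dropout rate, both in Section 10.4:

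- n = 450 × 0.80 = 360
- SD of each paired difference σ = 1
- d and s equal to 0 or ±0.3
- two-sided α of 0.05, or 0.05/36 = 0.00139 (one test per MOS-36 item)

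Power = Φ(|δ|√n/σ − z) + Φ(−|δ|√n/σ − z), where δ is the mean of the contrast. For |δ| = 0.3, |δ|√n/σ = 0.3 × 18.97 = 5.69. With z = 1.96 this gives Φ(3.73) ≈ 1.00. With z = 3.20 it gives Φ(2.49) ≈ 0.994. For δ = 0 the rejection rate is α.

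| Real change d | Shift s | Baseline vs 30 month (α 0.05; 0.05/36) | Baseline vs retrospective (α 0.05; 0.05/36) |
|---|---|---|---|
| 0.3 | 0 | 1.00; 0.994 | 0.05; 0.001 |
| 0 | 0.3 | 1.00; 0.994 | 1.00; 0.994 |
| −0.3 | 0.3 | 0.05; 0.001 | 1.00; 0.994 |

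With n = 382 (450 less 15%) the pattern is the same, and 0.994 becomes 0.996.

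**4. A smaller change.** Take d = 0.2 baseline SD, s = 0 and n = 360, with SD of the difference √(2(1 − r)) for a baseline-to-30-month correlation r. At r = 0.5 that SD is 1. A paired t-test of baseline versus 30 month then rejects 97% of the time at 0.05 and 72% at 0.05/36. For r from 0.4 to 0.6 the ranges are 93–99% and 60–85%.

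Row one of the table shows a shift flagged where there is none. Row three shows a shift missed. Row two shows that the written test does respond to a shift that nothing offsets.

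**The case against.** The best defence is that the intended contrast is stated twice, immediately before and after the disputed sentence. The second bullet continues a procedure whose preceding step defines shift as retrospective versus baseline, and the rule that follows is keyed to the same pair. A careful analyst would recover the intent, and loose wording for a form completed at the 30 month visit is a plausible explanation. This stands as a reason to call the matter minor. It does not make the sentence correct, because the closing paragraph uses '30 month' for the current-state answers.

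The consequence is also conditional. Read literally throughout, the section gives a test that feeds nothing and a rule that names the right pair. Harm arises only if the second bullet's test is used for the rule. Even then a false trigger costs little, because the ordinary baseline comparison is kept and another is added. A missed trigger matters more, since the retrospective comparison would be dropped.

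A reader might infer three stronger things that the protocol does not support:

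- **That the written test cannot detect response shift.** It can. In the section's own example, with status nearly unchanged and answers different, it would respond because of the shift. What it cannot do is isolate the shift.
- **That a shift hiding a true decline is the protocol's stated worry.** The worked example is apparent improvement with little objective change. The offsetting case is a scenario added here.
- **That the plan carries a 97% false-trigger rate.** That figure depends on an assumed n, correlation and effect, ignores the multiplicity adjustment the section promises, and applies only if the wrong test feeds the rule.

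**Conclusion.** The point holds as an internal inconsistency. The sentence specifying the response-shift test names a pair that matches neither the first bullet nor the decision rule. As worded, it tests real change and shift together and cannot isolate shift. This follows from the text and from the algebra of the three contrasts, without any numerical assumption beyond no recall error.

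The rejection rates only show direction. They rest on an assumed sample size, variance, correlation and effect, and on a Bonferroni divisor of 36 that the protocol does not name. They should not be quoted as properties of this trial.

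Severity is minor. One sentence is affected, in a check on one instrument within a secondary quality-of-life assessment. Section 9.1 does not expect these outcomes to be related to the primary one. The planned data collection is already right, and the primary MLD analysis is untouched.

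**What to change.** Replace the first sentence of the second bullet in Section 9.3 with wording such as: *For each MOS-36 question, a paired test will compare the answer given at baseline with the retrospective-baseline answer collected at the 30 month visit.* Keep baseline versus current-state 30 month answers as the ordinary change comparison, and do not use it as the test for shift. The rest of the bullet and the closing paragraph can stay as they are.

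The cost is one sentence. The retrospective form is already scheduled, so no visit, form or sample size changes. The correction should be made before the quality-of-life data are analysed.

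### As written, the section 9.3 reporting rule leaves out the 18 month MOS-36 collected from all women, so a woman without a 30 month form contributes nothing after baseline

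*Protocol*

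**What the plan says.** Protocol section 9.2 lists five quality of life instruments, the MOS-36 first, which "will be administered to all patients at randomization and at the 18 and 30 month visits". The quality of life row of Table 2 agrees.

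Section 9.3 adds a retrospective MOS-36 at one visit only: "at the 30 month visit, after the patient completes the MOS-36 form, she will be asked to fill it out again", this time as she felt at baseline. The reporting rule at the end of 9.3 then has two branches:

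- Domains with a significant response shift: "all further analyses for those domains on the MOS-36 will compare the 30 month results to the baseline and to the retrospective analyses".
- All other domains: "Otherwise, only comparisons between the 30 month and baseline responses will be reported".

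Section 9.1 gives the purpose as to "monitor the qualitative consequences of hormone replacement therapy and/or antioxidant treatment". It does not tie that purpose to one visit. Of the quality of life outcomes it also says: "They may, however, be related to mortality rate, and potential confounders such as treatment noncompliance". Section 10, on design and analysis, does not mention quality of life.

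**The concern.** The follow-up score in both branches is the 30 month score. The 18 month MOS-36 is collected from all women but enters no reported comparison if the rule is followed literally. A woman who dies, withdraws or misses the form between 18 and 30 months then adds nothing after baseline, although her 18 month answers are on file.

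Section 9.1 allows that quality of life may be related to mortality and noncompliance. Women missing at 30 months may therefore differ from those who remain, and a comparison restricted to 30 month completers is exposed to that difference. The data that would reduce the exposure are already being collected.

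**Working it through.** **1. What the rule covers**

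| MOS-36 form | Collected (9.2, 9.3) | Shift found | No shift found |
|---|---|---|---|
| Baseline | all women | used | used |
| 18 months | all women | not named | not named |
| 30 months | all women | used | used |
| Retrospective, at 30 months | all women | used | not used |

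The item-level tests earlier in 9.3 also name only baseline and 30 months. No other section gives the 18 month MOS-36 an analysis.

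**2. The protocol's own figures**

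There is no MOS-36 sample size or precision figure to reproduce. The figures borrowed below come from section 10.4 and concern MLD.

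- Sample size: 2 × (1.960 + 1.282)² / 0.334² rounds up to 189 per arm, 378 in total (stated 380).
- Dropout: 380 / 0.85 = 447.1, so 448 (stated 450).
- Power table with 20% loss: 0.812 at effect size 0.30 and N = 450 (stated 0.81); 0.879 at 0.35 and N = 400 (stated 0.88).

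**3. Women with an 18 month but no 30 month form (illustration)**

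Inputs: N = 450; dropout d = 15% or 20% (section 10.4); time base T = 40.5 months (section 10.2.1) or 36 months (last routine visit). Assumptions: the angiographic dropout rate applies to questionnaires, with constant hazard λ = −ln(1−d)/T. The number lost between the visits is 450 × (e^(−18λ) − e^(−30λ)).

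| d | T | Present at 18 m | Present at 30 m | Lost between |
|---|---|---|---|---|
| 15% | 40.5 | 418.6 | 399.0 | 19.7 |
| 15% | 36 | 414.9 | 393.0 | 21.9 |
| 20% | 40.5 | 407.5 | 381.4 | 26.1 |
| 20% | 36 | 402.5 | 373.6 | 28.9 |

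That is about 20 to 29 women, or 4-6% of 450.

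**4. Precision of the 30 month contrast**

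Assume an equal correlation ρ between any two visits; the protocol gives none. The partial correlation of the 18 and 30 month scores given baseline is R = (ρ − ρ²)/(1 − ρ²) = ρ/(1 + ρ). With monotone loss, the variance using the 18 month data, relative to 30 month completers alone, is (1 − R²) + R² × n30/n18.

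- d = 15%, T = 40.5: n30/n18 = 399.0/418.6 = 0.953. At ρ = 0.5, 0.6 and 0.7 the ratios are 0.995, 0.993 and 0.992.
- d = 20%, T = 36: n30/n18 = 373.6/402.5 = 0.928. The ratios are 0.992, 0.990 and 0.988.

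The gain is 0.5 to 1.2%. With complete data it is zero.

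**5. Precision of an effect averaged over 18 and 30 months**

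This is a different target. With unit variances and complete data:

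- Baseline-adjusted: 1 − ρ² for 30 months alone, (1 + ρ)/2 − ρ² for the two-visit mean.
- Change score: 2(1 − ρ) against 1.5(1 − ρ), a ratio of 0.75 at any ρ.

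| ρ | 30 m alone | Mean of two | Reduction |
|---|---|---|---|
| 0.3 | 0.91 | 0.56 | 38% |
| 0.5 | 0.75 | 0.50 | 33% |
| 0.6 | 0.64 | 0.44 | 31% |
| 0.7 | 0.51 | 0.36 | 29% |
| 0.8 | 0.36 | 0.26 | 28% |

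The range over both methods is 25-38%.

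**The case against.** The strongest reply is that the rule is being read out of context. It closes a section on response shift, straight after a sentence that adds the retrospective form as a comparator. There, *only* may mean no more than without the retrospective form, and 30 months may be named simply because the retrospective form exists at no other visit. Models, visits and missing-data handling for a secondary questionnaire are commonly left to a statistical analysis plan, and none is shown here.

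Much of this stands. A reader might infer that the 18 month form is deliberately discarded, or will never be analysed. The documents do not show that intent. But the protocol is not merely silent. It speaks of all further analyses in one branch and of the only reported comparisons in the other. An analysis plan that modelled the 18 month scores would depart from that wording. Even on the kinder reading, the 18 month form has no stated role.

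Three further objections are fair:

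- **Dropout.** The 15-20% was set for an outcome that needs an exit angiogram. A woman who declines the angiogram may still complete a questionnaire.
- **Deaths.** A repeated-measures model implicitly extends scores past death, so it does not remove that problem. The 18 month effect, reported separately, is not affected for women who die later.
- **Response shift at 18 months.** No retrospective form exists then, so shift cannot be checked. Reporting each visit separately leaves the 30 month contrast and its check intact.

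**Conclusion.** The point holds as a minor defect of wording with a real but modest consequence. Taken literally, both branches of the 9.3 rule omit the 18 month MOS-36, and women without a 30 month form drop out of every follow-up comparison. The main cost is avoidable exposure to missing-data bias. Its size cannot be derived from the protocol; the 20-29 women are an illustration resting on a borrowed dropout rate and a constant hazard.

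Stronger readings are not supported:

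- A reader might infer that every reported MOS-36 comparison is limited to 30 months versus baseline. Domains with response shift are also compared with the retrospective form.
- A reader might infer a large loss of precision. For the 30 month contrast, which is what the protocol reports, it is roughly 1%. The 25-38% applies only to an effect averaged over two visits, under equal correlations of 0.3-0.8.
- A reader might infer that section 9.1 expects quality of life to be related to mortality and noncompliance. It says only that it may be.

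The rule concerns the MOS-36 alone. It does not govern the other four instruments and has no bearing on the primary MLD analysis.

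**What to change.** In section 9.3:

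1. State that the rule decides only whether the comparison with the retrospective form is added at 30 months.
2. State that MOS-36 domain scores at 18 and 30 months are analysed in one repeated-measures model with the baseline score as covariate, so that women with either follow-up form are included.
3. Report the treatment effect at each visit, and keep the 30 month contrast together with its retrospective comparison where shift is found.
4. Optionally add an effect averaged over the two visits, noting that response shift cannot be checked at 18 months.

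The cost is a few sentences of protocol text and slightly more analysis. No new data, visits or patients are needed. The one small downside is the unchecked 18 month visit in any averaged effect.
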